8.8 SITE CLOSE-OUT

Upon completion of the study, the clinical monitor will conduct a final visit (close-out) at the site. At the time of the site close-out visit, the Monitor will collect all outstanding study documents, ensure that the Investigator's files are accurate and complete, review record retention requirements with the Investigator, make a final accounting of all study supplies, and ensure that all applicable requirements are met for the study. The observations and actions made at this visit will be documented in a final closeout report.

8.9 PROTOCOL AMENDMENTS

The Sponsor will document modifications to the protocol in the form of a written amendment. All protocol modifications must be approved by the IRB before implementation. In the case of a medical emergency, to remove immediate apparent hazard to subjects, a change may be made preferably after discussion with the Sponsor or its designee. In these instances, the IRB will be notified as soon as possible.

8.10 RECORD KEEPING AND RETENTION

Data generated for the study should be stored in a limited-access file area and be accessible only to representatives of the study site, the Sponsor and its representatives, and relevant health authorities/regulatory agencies. All reports and communications relating to study subjects will identify subjects only by initials and subject identification number. Complete subject

identification will be kept by the investigator. This information will be treated with strict adherence to professional standards of confidentiality.

All study-related records must be maintained for at least 2 years after the last approval of a marketing application in an ICH region and until there are no pending or contemplated marketing applications in an ICH region or at least 2 years have elapsed since the formal discontinuation of clinical development of the investigational product. The Sponsor will notify the Investigator when records are no longer needed. The Investigator will not discard any records without notifying the Sponsor. If the Investigator moves from the current investigational site, the Sponsor should be notified of the name of the person who will assume responsibility for maintenance of the records at the investigational site or the new address at which the records will be stored. The Investigator will notify the Sponsor as soon as possible in the event of accidental loss or destruction of any study documentation.

8.11 INVESTIGATOR FINAL REPORT

The investigator shall provide the IRB and the Sponsor with an accurate final report within 2 months after completion, termination, or discontinuation of the study. The final report may not precede final data submission which has not been monitored.

8.12 STUDY REPORT AND PUBLICATION

The results of the study may be submitted for publication. Upon the prior written consent of the Sponsor, the Investigator shall have the rights to publish papers related to the Study.

If written permission from the Sponsor is provided, the PI may publish and/or present the results of the study conducted at their site, provided that, prior to any such publication or presentation, the site and/or the PI shall provide the Sponsor with two (2) hard copies and one electronic copy of any materials intended for publication or presentation at least sixty (60) days prior to the submission of manuscripts. The Sponsor shall then have sixty (60) days from the receipt of such materials to review and provide the site and/or the PI with written comments.

## STUDY SYNOPSIS

Title	A Prospective, Multi-Center, Open-Label, Single-Arm Study to Evaluate the Safety and Technical Performance of the CathVision ECGenius® System
Investigational device	
The CathVision ECGenius® System is an electrophysiology (EP) recording system to be used in EP studies as a tool to monitor, display, and record signals of the heart and cardiac arrhythmias.
 
Intended Use	To acquire, amplify, digitize, stream atrial and ventricular intracardiac electrophysiology signals during cardiac electrophysiology studies and related procedures.
Objective	The primary objective is to evaluate the safety and technical performance of the CathVision ECGenius® System. The secondary objective is to benchmark the intracardiac electrogram signal quality compared to commercially available systems in patients undergoing assessment and ablation of cardiac arrhythmias.
Study Design	
A prospective, multi-center, open-label, single-arm study to evaluate the safety and technical performance of the CathVision ECGenius® system. Patients who are scheduled to undergo an EP procedure and meet the inclusion/exclusion criteria will be enrolled in the study. Intracardiac signals will be passively recorded using CathVision ECGenius® System in parallel with the commercial EP recording system.

Sample size	Up to 30 subjects shall be enrolled in the study.
Investigational Sites	Up to two (2) investigational sites in the United States.
Study Duration / Follow-up Period	Study enrollment is planned for 1-3 months.

Document no.:	Effective Date:	Version: 1
Author:	Approver:	Reviewer:

Primary Endpoint	
The Primary endpoint of the study will be evaluated as the safety and technical success of CathVision ECGenius® System to collect and record intracardiac signals during EP procedures. With focus on:
 
 
• To record and plot low voltage electrograms
 
• To assess the improved signal (better signal to noise ratio) compared with the standard signal
 
• To visualize the shape and timing of electrograms
 

Secondary Endpoint	
The Secondary endpoint of the study will be evaluated as the technical performance of CathVision ECGenius® System during routine EP procedures.
 
 
• To log time stamp for arrhythmia termination when termination is successful
 
• To confirm compatibility of CathVision ECGenius® system with commercially available 3D mapping systems and with available intracardiac catheters.
 
• To have no or minimal device malfunctions reported with the use of the CathVision ECGenius®
 

Entry Criteria	
Inclusion Criteria
 
Eligible subjects will meet ALL the following inclusion criteria:
 
 
1. Patient is scheduled for catheter ablation or diagnostic electrophysiology procedure.
 
2. At least 18 years of age.
 
3. Able and willing to provide informed consent or obtain consent from a legally authorized representative (LAR).
 
 
Exclusion Criteria
 
Eligible subjects will not meet ANY of the following exclusion criteria:
 
 
1. Patient inability to understand or refusal to sign informed consent.
 
2. Patient is a prisoner or under incarceration
 
3. Patients who in the opinion of the physician are not candidates for this study.
 

Document no.:	Effective Date:	Version: 1
Author:	Approver:	Reviewer:

## 1. Purpose

To define the use of statistical techniques in the evaluation and control of product and processes in order to ensure, with a high degree of confidence, that all products and processes meet requirements.

## 2. Scope

This document provides insight into the use of a series of characterization techniques. This procedure is applicable to all processes and operations which require the use of statistical rationales.

## 3. Definitions

None

## 4. Responsibilities

CathVision Clinical – responsible for determining the appropriate statistical techniques and rationale to be used for activities that require data analysis and determination of sampling sizes

CathVision Quality – responsible for reviewing the adequacy and appropriateness of the statistical techniques and sampling plans used in design verification and validation testing, process validations, and test protocols.

## 5. Procedure

### 5.1. Inclusions

Potential subjects must meet ALL of the following criteria to be eligible for inclusion in the study:

1. Patient is scheduled for catheter ablation or diagnostic electrophysiology procedure.
2. At least 18 years of age.
3. Able and willing to provide informed consent or obtain consent from a legally authorized representative (LAR).

### 5.2. Exclusions

1. Patient inability to understand or refusal to sign informed consent.
2. Patient is a prisoner or under incarceration
3. Patients who in the opinion of the physician are not candidates for this study.

### 5.3. Primary safety endpoints

Freedom from major adverse events, evaluated at hospital discharge.

Document no.:	Effective Date:	Version: 1
Author: [name]	Approver:	Reviewer:

## 5.4. Primary performance endpoints

The Primary Performance endpoint of study will be evaluated as technical success of CathVision ECGenius™ System to collect and record intracardiac signals during EP procedures. With focus on:

- To record and plot low voltage electrograms
- To assess the improved signal (better signal to noise ratio) compared with the standard signal
- To visualize the shape and timing of electrograms

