4.5 STUDY OUTCOMES

4.5.1 PRIMARY OUTCOME

The Primary endpoint of the study will be evaluated as the technical success of CathVision ECGenius® System to collect and record intracardiac signals during routine EP procedures. Specifically:

- To record and plot low voltage electrograms
- To assess the improved signal (better signal to noise ratio) compared with the standard signal
- To visualize the shape and timing of electrograms

A defined evaluation scale for CathVision ECGenius signal versus the standard of care signal will be defined as 1 (best) to 5 (worse) for different areas of interest. This evaluation will be done by the institution principal investigator for both signal and mapping if available.

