4.5.2 SECONDARY OUTCOME

The Secondary endpoint of the study will be evaluated as the technical performance of CathVision ECGenius® System during routine EP procedures.

- To log time stamp for arrhythmia termination when termination is successful
- To confirm compatibility of CathVision ECGenius® system with commercially available 3D mapping systems and with available intracardiac catheters.
- To have no or minimal device malfunctions reported with the use of the CathVision ECGenius

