6.6 DEVICE MALFUNCTIONS

Device deficiency is defined as an inadequacy of a medical device with respect to its identity, quality, durability, reliability, safety, or performance.

Note, device deficiencies include malfunctions and use errors. All device deficiencies that occur during the trial will be recorded.

Device malfunction: failure of an investigational medical device to perform per its intended purpose when used in accordance with the instructions for use.

User error: act or omission of an act that results in a different medical device response than intended by the manufacturer or expected by the user.

The Device Deficiency CRF is specific for reporting all device deficiencies, or malfunctions that occur during the trial, whether or not they were associated with an adverse event. Device Deficiency CRFs should be submitted to the Sponsor within 24 hours of the occurrence defining the device deficiency.

Anticipated device deficiencies and malfunctions with any standard of care EP system include but are not limited to:

- Catheter deflection deficiency or failure
- Malfunction of a catheter electrode
- Malfunction of a catheter temperature sensor
- Unexpected termination of ablation due to internal system error
- Failure to initiate ablation due to internal system error
- Temporary or sustained loss of catheter navigation/visualization capability/signal

Record any CathVision ECGenius® system deficiencies and malfunctions including but are not limited to:

- ECGenius® system issues (Cube® EPAMP/RecSW)
 - Not able to power on
 - Power indicators not on
 - Not able to connect to the standard of care EP system
 - Not able to retrieve signal from standard of care EP system
 - Not able to power down
 - Database issues
 - Backup data issues
 - Not possible to clear fault without reboot
- ECGenius® Recorder Software
 - Malfunction
 - Loss of power
 - Loss of wave form
 - Recording issues (interruption, stop)
 - Not able to create patient
 - Not able to save patient
 - Live Mode issues (not able to create/resume patient, etc)

- Review Mode issues (not able to retrieve a patient)
- SW crashes
- SW loses connection to EPAMP
- Limitation: Only possible to review the latest recording file, while streaming is active
- Bug: Not possible to use the notch filter, if high-pass and low-pass is set to ‘None’
- Host Computer Malfunctions
 - Not able to boot/start
- User errors
 - Not recording data

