7.2 DESCRIPTIVE ANALYSES

Continuous variables will be summarized using standard quantitative statistics: number of available observations, mean, standard deviation, median, quartiles, and range (minimum and maximum observed values). The number of missing observations, if any, will also be summarized.

Categorical variables will be summarized using classical frequency statistics: number of non-missing observations and percentages by categories. Number and percent of missing data, if any, will also be summarized.

There are no predefined criteria for terminating the study based on statistical outcomes. Missing data will not be replaced or imputed.

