## 5.6. Statistical analysis

Endpoint	Statistical method	Hypothesis & benchmark
Freedom from major adverse events, evaluated at hospital discharge.	
 
• Count number of AEs
 
• Percentage: [Procedures with AE] / [Total number of procedures]
 
	
 
• 3.5% of patients develop major AE within 30 days of procedure.
 
• Zero CathVision Cube-related AE are expected.
 

Recording low-voltage electrograms	
 
• Count number of low-voltage electrograms plotted in total
 
• Percentage: [Total number low-voltage electrogram plots] / [Total number of procedures]
 
• Physician user quantitatively score low-voltage electrogram plots on “ease” of interpretation of EGMs” [0-5] on CathVision Cube and on existing EP system 
 
○ 0: Impossible
 
○ 1: Very difficult
 
 
 
	
 
• At least one low-voltage electrogram plot per procedure
 
• CathVision not inferior to existing EP recording system
 

Document no.:	Effective Date:	Version: 1
Author: [name]	Approver:	Reviewer:

Endpoint	Statistical method	Hypothesis & benchmark
	
 
 2: Difficult
 
 3: Possible
 
 4: Easy
 
 5: Very easy
 
 
 
• Average physician score on CathVision ECGenius™ vs average physician score on existing EP system
 
	
Assessing the improved signal quality (baseline noise level peak-to-peak)	
 
• Peak-to-peak amplitude of baseline noise, on unipolar electrogram, at at least 1 site with low-voltage electrograms, and averaged if more than 1.
 
• Peak-to-peak amplitude of baseline noise, on bipolar electrogram, at at least 1 site with low-voltage electrograms, and averaged if more than 1.
 
• Non-inferior peak-to-peak amplitude of baseline noise to existing EP recording system.
 
	
 
• Hypothesis is below 50uV unipolar baseline noise peak-to-peak
 
• Hypothesis is below 20uV bipolar baseline noise peak-to-peak
 
• Hypothesis is non-inferior to existing EP recording system.
 

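### Technical success of recording is the primary performance endpoint, but SAP 5.6 never computes the proportion of procedures successfully recorded; its plots-per-procedure ratio is a mean count that can hide failures

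*SAP*

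**What the plan says.** - **Endpoint.** In SAP 5.4 the primary performance endpoint "will be evaluated as technical success of CathVision" ECGenius. Protocol 4.5.1 agrees: "The Primary endpoint of the study will be evaluated as the technical success of CathVision ECGenius® System to collect and record intracardiac signals". Neither says what makes a single procedure a success.
- **Recording row, SAP 5.6.** The statistic is "Percentage: [Total number low-voltage electrogram plots] / [Total number of procedures" (closing bracket follows). The benchmark beside it is "At least one low-voltage electrogram plot per procedure".
- **Score and noise rows, SAP 5.6.** Low-voltage plots are scored 0 to 5 for ease of interpretation on both systems and the averages are compared. Baseline noise is measured at one or more low-voltage sites. Both rows aim at non-inferiority to the existing system. Neither has a rule for a procedure without an ECGenius recording.
- **Missing data, Protocol 7.2.** "Missing data will not be replaced or imputed". The same section requires the amount of missing data to be summarized.
- **Device failures.** Protocol 6.6 has all device deficiencies recorded and lists, among others, software crashes, loss of connection to the amplifier and "Recording issues (interruption, stop" (closing bracket follows). Failure to record data is listed there as a user error. The related secondary outcome in Protocol 4.5.2 is "To have no or minimal device malfunctions reported with the use of the CathVision ECGenius". It has no row in SAP 5.6.

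**The concern.** An endpoint about whether the device records should yield a proportion: procedures recorded successfully over procedures attempted. SAP 5.6 gives a count of plots, a score, a noise level and an exploratory description of shape and timing.

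The count does not test its own benchmark, because extra plots in one procedure offset none in another. It also stops being informative once a procedure has one plot. The score and noise results exist only where ECGenius produced a trace, so missing values can be caused by the device under test. Failures are recorded as deficiencies, but nothing carries them into the primary endpoint.

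At stake is the main performance statement. The report could show a ratio well above 100% and favourable scores while a material share of recordings failed or were interrupted, and a reader could not recover the success rate from the planned primary results.

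**Working it through.** **Inputs.** N = 30 from SAP 5.5, the mean of three comparable trials: (30 + 20 + 40)/3 = 30. This reproduces. The statistic, benchmark and 0 to 5 scale are from SAP 5.6 and the no-imputation rule is from Protocol 7.2. The number of failed procedures f, the plots per working procedure k and a mean score of 4.2 in working procedures are my assumptions; the documents give none of them.

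**Formulas.**
- Success proportion = (30 − f)/30, with an exact (Clopper-Pearson) 95% CI.
- SAP ratio = k(30 − f)/30.
- Available-case mean score = 4.2 for any f.
- Mean score with failures at 0 = 4.2(30 − f)/30.

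| f | Success (exact 95% CI) | SAP ratio, k = 1 / 2 / 3 | Available-case score | Score, failures at 0 |
|---|---|---|---|---|
| 0 | 100% (88.4 to 100) | 100% / 200% / 300% | 4.20 | 4.20 |
| 3 | 90.0% (73.5 to 97.9) | 90% / 180% / 270% | 4.20 | 3.78 |
| 4 | 86.7% (69.3 to 96.2) | 87% / 173% / 260% | 4.20 | 3.64 |
| 5 | 83.3% (65.3 to 94.4) | 83% / 167% / 250% | 4.20 | 3.50 |
| 6 | 80.0% (61.4 to 92.3) | 80% / 160% / 240% | 4.20 | 3.36 |

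For f = 4 and k = 2: 2 × 26/30 = 52/30 = 173%, against 26/30 = 86.7%.

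**Reading the table.**
1. The ratio equals the success proportion only when every working procedure gives exactly one plot (k = 1).
2. With k = 2 the ratio stays at or above one plot per procedure as long as 2(30 − f)/30 ≥ 1, that is f ≤ 15. If the benchmark were judged on this ratio, half the procedures could fail and it would still be met.
3. The available-case score does not move with f.

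**Three kinds of procedure under the rules as written.**
- ECGenius never connects: no plot, so the per-procedure benchmark is missed. No score or noise value exists; it is counted as missing and not replaced.
- The software crashes after one plot: the benchmark is met, score and noise values exist, and nothing in the primary rows shows the interruption.
- ECGenius records throughout but the patient has no low-voltage site: no plot, so the benchmark is missed although the device worked.

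The recording row therefore cannot separate the first case from the third, or the second from a full success.

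**The case against.** The strongest defence is that SAP 5.6 does measure recording. The low-voltage row has all procedures in its denominator and a per-procedure benchmark, so an outright failure counts against the device. That stands. A reader might infer that no row addresses recording success, or that the whole endpoint describes only procedures in which the device worked; the documents do not support this. Conditioning on a working device applies to the score and noise rows. The fault in the recording row is that its statistic does not compute its benchmark.

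Second, a reader might infer that failures leave no trace in the score and noise results. Protocol 7.2 rules that out, because missing observations must be summarized. What it lacks is the reason: a value missing through device failure looks the same as one missing for any other cause.

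Third, no passage says that failed procedures are excluded from score and noise. I infer it from the no-imputation rule and the absence of a rule for failures. Nor do the documents say whether the two systems' averages are paired. If they are, the comparator's value drops out as well, so it cannot be said that only ECGenius benefits.

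Fourth, use errors are not lost: Protocol 6.6 counts them as device deficiencies and has them recorded. Whether an operator's failure to record is a technical failure of the device is a judgement that the plan should state.

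Fifth, simply entering 0 for an absent trace would conflict with the no-imputation rule, would mix availability with ease of interpretation, and has no counterpart in Protocol 4.5.1, where the scale runs from 1 (best) to 5 (worst). This limits the remedy to a sensitivity analysis. It does not remove the gap.

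**Conclusion.** The point holds in this form: the primary performance endpoint is technical success, success is not defined per procedure, and no planned statistic estimates its rate. The ratio in the recording row can exceed 100% and can hide failures (173% against 86.7% in the example with 4 failures). Interruptions after the first plot do not appear in the primary rows. The score and noise comparisons are conditional on a usable ECGenius trace.

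The size depends on assumed values of f and k and on the assumed mean score of 4.2. The table shows the mechanism and does not predict a failure rate. If every procedure is recorded in full, the gap does no harm to the result, although 30/30 would still carry a lower 95% limit of 88.4% that the plan does not call for. The study is descriptive, so no error rate is at issue, but this is its main performance claim and should be settled before analysis.

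**What to change.** 1. Add a first performance row to SAP 5.6: number and percentage of procedures with technical success, with an exact 95% CI, over all procedures in which ECGenius connection was attempted.
2. Define success as intracardiac signals recorded and saved through the planned parallel recording, without a Protocol 6.6 ECGenius deficiency that interrupts or loses the recording. State when that recording starts and ends, since Protocol 4.7.4 describes it only loosely. Show failures due to use error as a separate line within the total.
3. Replace plots over procedures with the proportion of procedures having at least one low-voltage plot, among those where the standard system shows a low-voltage electrogram. This separates device failure from absence of a site.
4. Keep the available-case score and noise results. Beside them, give the number of procedures missing because of device failure. Add a sensitivity analysis of the score with failed recordings in the worst category, after reconciling the SAP scale of 0 to 5 with the Protocol 4.5.1 scale, which runs in the opposite direction.
5. For the secondary outcome, report the count and percentage of procedures with at least one ECGenius malfunction in place of the undefined minimal number.

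**Cost.** A SAP revision, and probably small clarifications to Protocol 7.2 (so that the sensitivity analysis is allowed) and 4.5.1 (the scale). Deficiencies are already recorded, but the documents do not show whether the case report form captures connection attempts and interruption of recording, so that must be checked. Reported performance may look slightly less favourable.

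### The SAP row for the improved-signal item tests baseline noise for non-inferiority without a margin, so meeting it does not show an improved signal or a better signal-to-noise ratio

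*SAP*

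**What the plan says.** SAP 5.4 lists three focus items for the primary performance endpoint. The second is "To assess the improved signal (better signal to noise ratio) compared with the standard signal". Protocol 4.5.1 and both synopses carry the same item. It names a quantity (SNR), a direction (better) and a comparator (the standard signal).

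The matching row of the table in SAP 5.6, the third, is labelled "Assessing the improved signal quality (baseline noise level peak-to-peak". It measures baseline noise on unipolar and bipolar electrograms at one or more low-voltage sites, averaged if there are several, and adds "Non-inferior peak-to-peak amplitude of baseline noise to existing EP recording system". Its hypotheses are:

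- "Hypothesis is below 50uV unipolar baseline noise peak-to-peak"
- "Hypothesis is below 20uV bipolar baseline noise peak-to-peak"
- "Hypothesis is non-inferior to existing EP recording system"

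Two other comparisons of the systems exist, both subjective. The second row of SAP 5.6 scores ease of interpretation from 0 to 5, with the benchmark "CathVision not inferior to existing EP recording system". Protocol 4.5.1 adds an investigator rating: "A defined evaluation scale for CathVision ECGenius signal versus the standard of care signal will be defined as 1 (best) to 5 (worse". The first has no margin and the second has no criterion.

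Protocol 7.1 says that no formal hypothesis lies behind the sample size, and Protocol 7.2 plans descriptive summaries. Protocol 4.2 and 4.7.4 plan recording in parallel with the standard system and a comparison of the two recordings after the procedure.

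**The concern.** The item asks whether the ECGenius signal is better than the standard one. The hypotheses in its row ask whether noise is below two fixed levels and not worse than the comparator by some unstated amount. The idea of improvement survives only in the row's label. Neither document defines a signal amplitude, computes an SNR, or states what result would count as improved.

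What is at stake is the claim. Improved signal quality is the sponsor's development goal in Protocol 1.3. A row labelled as improved signal quality and reported as met could be read as evidence of a gain, although the row can be met with none.

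**Working it through.** **1. The plan's own figure.** SAP 5.5 takes 30 as the average of three trials: (30 + 20 + 40)/3 = 30. This reproduces, but it says nothing about precision for noise or SNR.

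**2. Item and row side by side.**

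| | Focus item (SAP 5.4) | Third row of SAP 5.6 |
|---|---|---|
| Quantity | SNR | Peak-to-peak baseline noise |
| Comparator | Standard signal | None for the two cut-offs; existing system for the third hypothesis |
| Direction | Better | Below a fixed level; non-inferior |
| Margin, interval or improvement criterion | None | None |

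**3. Can the row be met with no improvement?** Take equal noise on both systems (illustrative values): 18 µV bipolar and 40 µV unipolar.

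- Bipolar: 18 < 20, met.
- Unipolar: 40 < 50, met.
- Noise ratio: 18/18 = 1 and 40/40 = 1. Non-inferiority is true at equality, whatever margin is meant.
- Improvement: 0%.

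**4. When does noise stand in for SNR?** Let A be signal amplitude, N noise, E ECGenius and C the comparator.

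SNR_E / SNR_C = (A_E / A_C) × (N_C / N_E)

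If both systems record the same electrodes with the same filtering, A_E ≈ A_C and the SNR ratio is roughly the inverse of the noise ratio. If filtering differs, amplitude can differ too. With assumed amplitudes at the same 15 µV noise, 500/15 = 33.3 but 250/15 = 16.7. Equal noise then hides a twofold difference in SNR. Parallel recording makes shared electrodes plausible, but the SAP requires neither the same electrodes nor the same filters.

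**5. What could a paired analysis show?** Let d = log(N_E / N_C), averaged within procedure. The 95% CI for the ratio is exp(mean d ± t × SD/√n). It lies wholly below 1 only if the observed ratio is below exp(−t × SD/√n). The documents give no SD, so the SDs below are assumed. Thirty is a ceiling: enrolment is up to 30, and screen failures after the screening visit count towards it (Protocol 4.7.3). Twenty pairs is an assumed lower case.

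| Assumed SD of d | exp(t × SD/√n), n = 30 (t = 2.045) | Observed noise ratio must be below | exp(t × SD/√n), n = 20 (t = 2.093) | Observed noise ratio must be below |
|---|---|---|---|---|
| 0.2 | 1.078 | 1/1.078 = 0.93 | 1.098 | 1/1.098 = 0.91 |
| 0.3 | 1.119 | 1/1.119 = 0.89 | 1.151 | 1/1.151 = 0.87 |
| 0.5 | 1.205 | 1/1.205 = 0.83 | 1.264 | 1/1.264 = 0.79 |

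The same factors bear on a non-inferiority margin. At an observed ratio of 1.00 the upper 95% limit equals the factor, so equal observed noise passes only if the margin exceeds about 8%, 12% or 21% (30 pairs), or 10%, 15% or 26% (20 pairs).

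**The case against.** The strongest case for the plan has four parts.

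- **The item is not a superiority hypothesis.** It is worded as something to assess, within technical success, in a largely descriptive study. This stands: the point is not a missing powered test. But SAP 5.6 has a hypothesis column and fills it for this row, and none of the three hypotheses concerns improvement.
- **The planned data could still show a gain.** Noise is compared with the existing system, Protocol 7.2 gives the summaries, and the investigator rates one signal against the other. This also stands. A reader might infer that the study is incapable of showing improvement; the documents do not support that. What is missing is a criterion linking those data to the claim.
- **Noise is a reasonable surrogate, and the row's label says so.** This is right when electrodes and filters match. Parallel recording, and the listing in Protocol 6.6 of failure to retrieve the standard system's signal as a deficiency, point towards shared signals. They do not settle filtering. Even a perfect surrogate leaves the hypothesis at non-inferiority.
- **The cut-offs prove nothing about the comparator.** They are looser than the levels Protocol 1.3 calls best-in-class (20 against 15 µV bipolar, 50 against 30 µV unipolar). A reader might infer that a passing device could have a quantifiably worse SNR than the comparator. That does not follow: the documents give no comparator noise and do not present those levels as the comparator's, and the third hypothesis would have to fail to bind. No size of SNR loss can be derived.

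**Conclusion.** The point holds as a mismatch between an endpoint item and its stated analysis. All three hypotheses of the row are satisfied at equal noise, that is, at 0% improvement. Meeting the row therefore does not show an improved signal or a better SNR, and the undefined margin leaves open how much worse would still count as non-inferior. This rests only on the wording of SAP 5.4 and 5.6 and Protocol 4.5.1; the 18 and 40 µV values are an illustration. The thresholds in the last step of the working rest on assumed SDs and numbers of pairs.

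It should be corrected, but its reach is limited: one of three performance focus items and the claim drawn from it. It does not show that ECGenius is noisier than the comparator, or that noise is the wrong thing to measure.

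**What to change.** Make the change in the SAP before any comparative data are examined.

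**Preferred.** In the third row of SAP 5.6:

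- Measure baseline noise on both systems at the same electrode or pair, in the same time window, separately for unipolar and bipolar. Match the filter and notch settings, or at least record them.
- State that noise is the surrogate for SNR under these conditions, or compute SNR directly where a signal amplitude can be defined.
- Average within procedure and report the within-procedure ECGenius/comparator noise ratio with a 95% CI.
- Call a recording type improved only if its CI lies wholly below 1 (above 1 for an SNR ratio) and settings were matched. Otherwise report descriptively.
- Keep the 50 and 20 µV cut-offs as supporting measures.

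**Fallback, if comparator recordings cannot be analysed this way.** Remove the claims of an improved signal and a better SNR from both documents. If some comparator noise measure remains, reword the item as non-inferior baseline noise with a stated margin. If none remains, reword it as baseline noise against the absolute cut-offs.

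**Cost.** No extra patients or procedures. The preferred option needs some extra signal analysis and depends on comparator files being exportable, which the documents do not state. The claim may become less favourable, and with at most 30 pairs a small real gain may not be shown. The fallback is mainly a text change.
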